14.1.3.2.9 Sensitivity analyses

This section outlines the possible event and censoring dates for progression, as well as addresses the issues of missing tumor assessments during the study. For instance, if one or more assessment visits are missed prior to the progression event, to what date should the progression event be assigned? And should progression event be ignored if it occurred after a long period of a patient being lost to follow-up? It is important that the protocol and RAP specify the primary analysis in detail with respect to the definition of event and censoring dates and also include a description of one or more sensitivity analyses to be performed.

Based on definitions outlined in [Section 14.1.3.2.7](#), and using the draft FDA guideline on endpoints (Clinical Trial Endpoints for the Approval of Cancer Drugs and Biologics, April 2005) as a reference, the following analyses can be considered:

Table 14-5 Options for event dates used in PFS, TTP, duration of response

Situation		Options for end-date (progression or censoring) ¹ (1) = default unless specified differently in the protocol or RAP	Outcome
A	No baseline assessment	(1) Date of randomization/start of treatment ³	Censored
B	Progression at or before next scheduled assessment	(1) Date of progression (2) Date of next scheduled assessment ²	Progressed Progressed
C1	Progression or death after exactly one missing assessment	(1) Date of progression (or death) (2) Date of next scheduled assessment ²	Progressed Progressed
C2	Progression or death after two or more missing assessments	(1) Date of last adequate assessment ² (2) Date of next scheduled assessment ² (3) Date of progression (or death)	Censored Progressed Progressed
D	No progression	(1) Date of last adequate assessment	Censored
E	Treatment discontinuation due to ‘Disease progression’ without documented progression, i.e. clinical progression based on investigator claim	(1) N/A (2) Date of discontinuation (visit date at which clinical progression was determined)	Ignored Progressed
F	New anticancer therapy given	(1) Date of last adequate assessment (2) Date of secondary anti-cancer therapy (3) Date of secondary anti-cancer therapy (4) N/A	Censored Censored Event Ignored
G	Deaths due to reason other than deterioration of ‘Study indication’	(1) Date of last adequate assessment	Censored (only TTP and duration of response)

¹. =Definitions can be found in [Section 14.1.3.2.7](#)

². =After the last adequate tumor assessment. "Date of next scheduled assessment" is defined in [Section 14.1.3.2.7](#).

³. =The rare exception to this is if the patient dies no later than the time of the second scheduled assessment as defined in the protocol in which case this is a PFS event at the date of death.

The primary analysis and the sensitivity analyses must be specified in the protocol. Clearly define if and why options (1) are not used for situations C, E and (if applicable) F.

Situations C (C1 and C2): Progression or death after one or more missing assessments: The primary analysis is usually using options (1) for situations C1 and C2, i.e.

- (C1) taking the actual progression or death date, in the case of only one missing assessment.
- (C2) censoring at the date of the last adequate assessment, in the case of two or more consecutive missing assessments.

In the case of two or missing assessments (situation C2), option (3) may be considered jointly with option (1) in situation C1 as sensitivity analysis. A variant of this sensitivity analysis consists of backdating the date of event to the next scheduled assessment as proposed with option (2) in situations C1 and C2.

Situation E: Treatment discontinuation due to ‘Disease progression’ without documented progression: By default, option (1) is used for situation E as patients without documented PD should be followed for progression after discontinuation of treatment. However, option (2) may be used as sensitivity analysis. If progression is claimed based on clinical deterioration instead of tumor assessment by e.g. CT-scan, option (2) may be used for indications with high early progression rate or difficulties to assess the tumor due to clinical deterioration.

Situation F: New cancer therapy given: the handling of this situation must be specified in detail in the protocol. However, option (1), i.e. censoring at last adequate assessment may be used as a default in this case.

Additional suggestions for sensitivity analyses

Other suggestions for additional sensitivity analyses may include analyses to check for potential bias in follow-up schedules for tumor assessments, e.g. by assigning the dates for censoring and events only at scheduled visit dates. The latter could be handled by replacing in [Table 14-5](#) the “Date of last adequate assessment” by the “Date of previous scheduled assessment (from baseline)”, with the following definition:

- **Date of previous scheduled assessment (from baseline)** is the date when a tumor assessment would have taken place, if the protocol assessment scheme was strictly followed from baseline, immediately before or on the date of the last adequate tumor assessment.

In addition, analyses could be repeated using the Investigators’ assessments of response rather than the calculated response. The need for these types of sensitivity analyses will depend on the individual requirements for the specific study and disease area and have to be specified in the protocol or RAP documentation.

14.1.4 Data handling and programming rules

The following section should be used as guidance for development of the protocol, data handling procedures or programming requirements (e.g. on incomplete dates).

14.1.4.1 Study/project specific decisions

For each study (or project) various issues need to be addressed and specified in the protocol or RAP documentation. Any deviations from protocol must be discussed and defined at the latest in the RAP documentation.

The proposed primary analysis and potential sensitivity analyses should be discussed and agreed with the health authorities and documented in the protocol (or at the latest in the RAP documentation before database lock).

14.1.4.2 End of treatment phase completion

Patients **may** voluntarily withdraw from the study treatment or may be taken off the study treatment at the discretion of the investigator at any time. For patients who are lost to follow-up, the investigator or designee should show "due diligence" by documenting in the source documents steps taken to contact the patient, e.g., dates of telephone calls, registered letters, etc.

The end of treatment visit and its associated assessments should occur within 14 days of the last study treatment.

Patients may discontinue study treatment for any of the following reasons:

- Adverse event(s)
- Lost to follow-up
- Physician decision
- Pregnancy
- Protocol deviation
- Subject/guardian decision
- Death
- Progressive disease per irRC (not per RECIST)
- Study terminated by the sponsor

14.1.4.3 End of post-treatment follow-up (study phase completion)

End of post-treatment follow-up visit will be completed after discontinuation of study treatment and post-treatment evaluations but prior to collecting survival follow-up.

Patients may provide study phase completion information for one of the following reasons:

- Adverse event
- Lost to follow-up
- Physician decision
- Pregnancy
- Protocol deviation

- Technical problems
- Subject/guardian decision
- Death
- New therapy for study indication
- Progressive disease
- Study terminated by the sponsor

14.1.4.4 Medical validation of programmed overall lesion response

As RECIST is very strict regarding measurement methods (i.e. any assessment with more or less sensitive method than the one used to assess the lesion at baseline is considered UNK) and not available evaluations (i.e. if any target or non-target lesion was not evaluated the whole overall lesion response is UNK unless remaining lesions qualified for PD), these UNK assessments may be re-evaluated by clinicians at Novartis or external experts. In addition, data review reports will be available to identify assessments for which the investigators' or central reader's opinion does not match the programmed calculated response based on RECIST criteria. This may be queried for clarification. However, the investigator or central reader's response assessment will never be overruled.

If Novartis elect to invalidate an overall lesion response as evaluated by the investigator or central reader upon internal or external review of the data, the calculated overall lesion response at that specific assessment is to be kept in a dataset. This must be clearly documented in the RAP documentation and agreed before database lock. This dataset should be created and stored as part of the 'raw' data.

Any discontinuation due to 'Disease progression' without documentation of progression by RECIST criteria should be carefully reviewed. Only patients with documented deterioration of symptoms indicative of progression of disease should have this reason for discontinuation of treatment or study evaluation.

14.1.4.5 Programming rules

The following should be used for programming of efficacy results:

14.1.4.5.1 Calculation of 'time to event' variables

Time to event = end date - start date + 1 (in days)

When no post-baseline tumor assessments are available, the date of randomization/start of treatment will be used as end date (duration = 1 day) when time is to be censored at last tumor assessment, i.e. time to event variables can never be negative.

14.1.4.5.2 Incomplete assessment dates

All investigation dates (e.g. X-ray, CT scan) must be completed with day, month and year.

If one or more investigation dates are incomplete but other investigation dates are available, this/these incomplete date(s) are not considered for calculation of the assessment date (and

assessment date is calculated as outlined in [Section 14.1.3.2.7](#)). If all measurement dates have no day recorded, the 1st of the month is used.

If the month is not completed, for any of the investigations, the respective assessment will be considered to be at the date which is exactly between previous and following assessment. If a previous and following assessment is not available, this assessment will not be used for any calculation.

14.1.4.5.3 Incomplete dates for last known date patient alive or death

All dates must be completed with day, month and year. If the day is missing, the 15th of the month will be used for incomplete death dates or dates of last contact.

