14.1.3.2.2 Overall survival

All patients should be followed until death or until patient has had adequate follow-up time as specified in the protocol whichever comes first. The follow-up data should contain the date the patient was last seen alive / last known date patient alive, the date of death and the reason of death (“Study indication” or “Other”).

Overall survival (OS) is defined as the time from date of randomization/start of treatment to date of death due to any cause. If a patient is not known to have died, survival will be censored at the date of last known date patient alive.

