- Date of last contact is defined as the last date the patient was known to be alive. This corresponds to the latest date for either the visit date, lab sample date or tumor assessment date. If available, the last known date patient alive from the survival follow-up page is used. If no survival follow-up is available, the date of discontinuation is used as last contact date.
- Date of secondary anti-cancer therapy is defined as the start date of any additional (secondary) antineoplastic therapy or surgery.

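### The rule that sets a death date with a missing day to the 15th has no stated lower bound, so in uncommon cases it dates a death before a documented contact or gives a negative OS.

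*Protocol*

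**What the plan says.** Protocol 14.1.4.5.3 first asks for complete data: "All dates must be completed with day, month and year". It then gives the fallback: "If the day is missing, the 15th of the month will be used for incomplete death dates or dates of last contact". The fallback carries no condition.

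The related definitions are also in Appendix 1:

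- **OS (14.1.3.2.2):** "Overall survival (OS) is defined as the time from date of randomization/start of treatment to date of death due to any cause". Death from any cause is also a PFS event (14.1.3.2.1).
- **Duration (14.1.4.5.1):** end date minus start date plus 1, in days. The same section has a sentence on patients with no post-baseline assessment, which ends "when time is to be censored at last tumor assessment, i.e. time to event variables can never be negative".
- **Last contact (14.1.3.2.7):** "Date of last contact is defined as the last date the patient was known to be alive", and "This corresponds to the latest date for either the visit date, lab sample date or tumor assessment date". The date on the survival follow-up page is used instead if there is one. Nothing links this date to an imputed death date.

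In the SAP, section 5.1 has no rule for death or last-contact dates. Section 5.1.6 covers only diagnosis, recurrence or progression, and relapse dates. Section 2.7.3 gives PFS censoring rules but no date rule for OS.

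**The concern.** The 15th is a conventional choice, and the difficulty is only that it applies whatever else is known about the patient. A stable-disease scan on 24 June followed by a death in June with no recorded day produces a death on 15 June, nine days before the scan. A patient who dies in the month of first dose can be recorded as dead before treatment began.

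The SAP guards against this for other dates. Imputed AE start dates that may fall after treatment start are kept after the first dose (5.1.2). Imputed prior-therapy end dates cannot pass the start of treatment (5.1.4). Post-treatment therapies in the same month as treatment end are placed after that end (5.1.5). Death dates have no such bound, although they feed both OS and PFS. At stake are impossible or backdated times in individual records.

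**Working it through.** **Inputs.** The duration formula (14.1.4.5.1), the 15th-of-month rule (14.1.4.5.3), and OS from start of treatment to death (14.1.3.2.2).

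**The plan's own figure.** Section 14.1.4.5.1 gives a duration of 1 day when the end date equals the start date. The formula agrees: 0 + 1 = 1.

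**Death in the month of first dose, day missing.** OS = 15 - (day of first dose) + 1.

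| Day of first dose | OS (days) |
|---|---|
| 15 | 1 |
| 16 | 0 |
| 17 | -1 |
| 20 | -4 |
| 31 | -15 |

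OS is therefore negative whenever the first dose is on the 17th or later.

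**Death after a late-month contact, day missing.** Any contact on the 16th or later of the month of death comes after the imputed death. The gap is (day of contact) - 15, so at most 31 - 15 = 16 days. Example in a non-leap year: first dose 2 January, visit 26 March, true death 29 March.

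- Imputed death is 15 March, 26 - 15 = 11 days before the visit.
- OS under the rule is 72 + 1 = 73 days. The true OS is 86 + 1 = 87 days.
- With the visit date + 1 as lower bound, death is 27 March and OS is 84 + 1 = 85 days.

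**The first-dose example with a lower bound.** First dose 20 March, visit 27 March, death in March. The last alive date + 1 is 28 March, so OS = 28 - 20 + 1 = 9 days, against -4 under the rule.

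**How often, given a missing day.** The documents give no frequency, so this rests on assumptions: the true death day is uniform over 1 to 30, and the gap from last contact to death is uniform over 0 to g days, with g at least 14. A death on day 15 + k (k = 1 to 15) is misplaced when the gap is 0 to k - 1 days. That is k of the g + 1 possible gaps, and the k sum to 120. So P = 120 / (30 x (g + 1)).

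| Largest gap g (days) | P(imputed death precedes last contact) |
|---|---|
| 14 | 120/450 = 26.7% |
| 28 | 120/870 = 13.8% |
| 45 | 120/1380 = 8.7% |
| 90 | 120/2730 = 4.4% |

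**Average error over all incomplete death dates.** Under the same uniform model the mean true day is (1 + 30)/2 = 15.5, so the 15th is on average 0.5 day early.

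**The case against.** **The 15th is only a fallback.** Complete dates are required, the eCRF has automatic discrepancy checks (Protocol 9.3), and missing values are queried (9.4). Deaths are recorded on a dedicated form (8.1.1). This stands as a reason to expect few cases. Survival follow-up can be by telephone every 3 months (7.1.5), which makes partial dates possible, but the documents do not show that they will be common.

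**Appendix 1 is general guidance.** Section 14.1.4 describes itself that way, 14.1.4.5.5 says programs must be adapted to the study, and the SAP introduction places derived-variable detail in a separate programming specification. That specification is not available here and may contain a guard. The finding is therefore limited to the protocol and SAP, which contain none.

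**Negative times are already excluded.** A reader might infer that 14.1.4.5.1 flatly contradicts the rule, because it says "time to event variables can never be negative". The full sentence concerns censoring at the last tumor assessment. It gives no mechanism for deaths, so it does not repair the rule, and its scope is too narrow to count as a clean general contradiction.

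**The problem is large.** A reader might take the 26.7% above as its size. That figure assumes a contact within 14 days before death, and it is conditional on a missing day. Gaps that short are typical on treatment, where visits are frequent and a missing death day is least likely. With gaps of up to 90 days, closer to the telephone schedule, the same model gives 4.4%.

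**Survival is biased downward.** This holds only for patients seen alive after the 15th. Over all incomplete death dates the average error is close to zero.

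**Conclusion.** The point holds as a minor one. Followed exactly, the written rule can date a death up to 16 days before a documented contact. It gives a negative OS, down to -15 days, when the first dose falls on the 17th or later of the month of death. These results need only the protocol's formula and a missing death day.

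The number of affected patients is unknown, and the percentages above are illustrations under stated assumptions. OS and PFS are secondary and are summarised by Kaplan-Meier medians with 90% confidence intervals (SAP 2.7.2). The ORR, CBR and DLT analyses do not use death dates imputed this way, and no decision rule depends on OS. The documents do not support a claim that survival results as a whole would be materially distorted.

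For last contact, the 15th can credit up to 14 unobserved days. A reader might infer that the 1st of the month should replace it, but that would exchange possible over-crediting for systematic under-crediting. The documents give no reason to prefer it.

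**What to change.** Add to SAP 5.1.6:

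- **Death, day missing:** use the later of the 15th and the last documented alive date + 1 day, capped at the end of that month and at the data cut-off. The last documented alive date is the latest complete date of any dose, visit, laboratory sample, scan or other contact.
- **Last contact, day missing:** keep the 15th, but do not let the imputed date fall before the latest complete date known alive or after the data cut-off.

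With the month-end cap, a first dose on 31 March and a death in March with no other contact gives 31 - 31 + 1 = 1 day, so OS cannot fall below 1 when the death month is on or after the month of first dose and the first dose is on or before the cut-off.

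The cost is a few lines of SAP text and a small change to the derivation program. No new data are needed. If the programming specification already has such a bound, the change is only to state it in the SAP.

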14.1.4.5.4 Non-target lesion response

If no non-target lesions are identified at baseline (and therefore not followed throughout the study), the non-target lesion response at each assessment will be considered 'not applicable (NA)'.

14.1.4.5.5 Study/project specific programming

The standard analysis programs need to be adapted for each study/project.

14.1.4.5.6 Censoring reason

In order to summarize the various reasons for censoring, the following categories will be calculated for each time to event variable based on the treatment completion page, the study evaluation completion page and the survival page.

For survival the following censoring reasons are possible:

- Alive
- Lost to follow-up

For PFS and TTP (and therefore duration of responses) the following censoring reasons are possible:

- Ongoing without event
- Lost to follow-up
- Withdrew consent
- Adequate assessment no longer available*
- Event documented after two or more missing tumor assessments (option
- Death due to, see [Table 14-5](#)) to reason other than underlying cancer (*only used for TTP and duration of response*)
- Initiation of new anti-cancer therapy

*Adequate assessment is defined in [Section 14.1.3.2.7](#). This reason is applicable when adequate evaluations are missing for a specified period prior to data cut-off (or prior to any other censoring reason) corresponding to the unavailability of two or more planned tumor assessments prior to the cut-off date. The following clarifications concerning this reason should also be noted:

- This may be when there has been a definite decision to stop evaluation (e.g. reason="Sponsor decision" on study evaluation completion page), when patients are not followed for progression after treatment completion or when only UNK assessments are available just prior to data cut-off).
- The reason "Adequate assessment no longer available" also prevails in situations when another censoring reason (e.g. withdrawal of consent, loss to follow-up or alternative anti-cancer therapy) has occurred more than the specified period following the last adequate assessment.
- This reason will also be used to censor in case of no baseline assessment.

14.2.1 Introduction

The currently used immune-related response criteria (irRC) uses unidimensional measurements to assess tumor response and it is an adaptation of the original irRC published by Wolchok (Wolchok 2009, Nishino 2013).

The purpose of this document is to summarize the irRC guidelines in details focusing on differences in tumor response assessments between irRC and RECIST v1.1.

The primary difference between irRC and RECIST 1.1 is the definition of progressive disease. The definitions of baseline target/non target lesions, number of lesions selected at baseline, the criteria for lesion measurement method of evaluation of response and definition of response are the same for irRC and RECIST 1.1 and are available in the RECIST 1.1 guidelines (Appendix 1).

14.2.2 New lesions and non-target lesions

In irRC a new lesion does not automatically indicate progressive disease.

New measurable lesions are added to the sum of diameters of the previously existing target lesions, and the sum of diameters is followed at each subsequent tumor assessment.

New measurable lesions are defined using the same criteria as for baseline target lesions in RECIST v1.1. New measurable lesions shall be prioritized according to size, and the largest lesions shall be selected as new measurable lesions. Up to five new measurable (and a maximum of two per organ) are allowed in total and will be included in the overall tumor assessment.

Non-target lesions (baseline and new non-measurable lesions) are used primarily for determination of Complete Response (CR). The RECIST v1.1 definitions for the assessment of non-target lesions apply. A CR requires that all non-target lesions disappear (both those present at baseline and any new non-measurable lesions that have appeared during the study). If after worsening a non-target lesion becomes measurable, it should still be followed as a non-target lesion. Worsening of non-target lesions and new non-measurable lesions only indicate disease progression if there is unequivocal evidence of disease progression (Table 14-6).

